12.1.1.2 Neurotoxicity

If any signs of \geq Grade 3 neurotoxicity occur, cisplatin use should be discontinued. In this instance, cisplatin should be replaced with carboplatin at a dose of 5 AUC (carboplatin dose = $5 \times [GFR+25]$).

12.1.1.3 Renal Toxicity

Cisplatin should be administered on the scheduled day of treatment using the following guidelines.

Creatinine Clearance	Cisplatin Dose
> 60 mL/min	100 mg/m ² *
50-60 mL/min	50 mg/m ²
< 50 mL/min	Discontinue and notify Medical Monitor Switch to carboplatin AUC = 5

In the event that GFR <50 mL/min, substitute carboplatin 5 AUC for cisplatin. Carboplatin is contraindicated if GFR < 30mL/min.

12.1.1.4 Mucositis

Grade 4 mucositis will require a permanent 25% dose reduction of cisplatin.

12.1.1.5 Ototoxicity

Ototoxicities, including clinical hearing loss not requiring a hearing aid or tinnitus that interferes with activities of daily living, should lead to discontinuation of cisplatin and substitution with carboplatin at a dose of AUC = 5.

12.1.2 Dose Modifications for Carboplatin

ANC/ μ L	Platelet/ μ L	Neurotoxicity, Grade	% Dose Administered
>2000	100,000	0, 1	100
1000 to 1999	75 000 to 100 000	2	50
<1000	<75 000	3, 4	hold for 1 week

12.1.3 Criteria for Retreatment

Following the first dose of cisplatin and the first dose of MK-3475, 2 further doses of cisplatin or carboplatin and 6 additional doses of MK-3475 will be given. Cisplatin or carboplatin will be given concurrently with radiation to a total of 70 Gy. These subsequent doses are at the discretion of the investigator and consent from the patient. If the patient meets any of the following criteria, treatment will be delayed 1 week and the patient will be re-evaluated.

- Neutrophils $\leq 1,500/\text{mm}^3$
- Platelets $\leq 75,000/\text{mm}^3$
- Grade 3 - 4 hematologic toxicities

- Grade 3 - 4 non-hematologic toxicities

Initiation of cisplatin or carboplatin re-treatment may be delayed for a maximum of 14 days to allow recovery from any toxicity. If the toxicity has not resolved within 14 days of the planned treatment date, re-treatment may occur if the patient is responding to treatment and there is agreement with the Trial Steering Committee.

12.1.4 Dose-Limiting Toxicity of Chemoradiotherapy

The definition of DLT will follow the generally accepted parameters in published phase I trials and will aim to identify any amplification of the expected toxicities of standard chemoradiotherapy by addition of pembrolizumab. The DLT period will be up until 6 weeks after the end of chemoradiotherapy. Therefore, DLT will be defined as: Grade 4 thrombocytopenia (or Grade 3 with haemorrhage); Grade 4 neutropenia lasting >7 days (or Grade 3 with fever); Grade 4 anaemia; Grade 4 mucositis (or Grade 3 with confluent lesions lasting >6 weeks after the end of radiotherapy); >2 weeks toxicity-related treatment delay; or any other ≥Grade 3 non-hematologic toxicity (except nausea and vomiting) which in the opinion of the investigator is considered dose-limiting.

12.2 APPENDIX 2: Common Terminology Criteria for Adverse Events V4.0 (CTCAE)

The descriptions and grading scales found in the revised NCI Common Terminology Criteria for Adverse Events (CTCAE) version 4.0 will be utilized for adverse event reporting. (<http://ctep.cancer.gov/reporting/ctc.html>)

12.3 APPENDIX 3: LENT SOMA Scales for all Anatomical Sites

This study will utilize the LENT SOMA radiation toxicity grading system (Int. J. Radiation Oncology Biol. Phys., Vol. 31, No. 5, 1049-1091, 1995).

All appropriate treatment areas should have access to a copy of the LENT SOMA scoring system.

12.4 APPENDIX 4: Response Evaluation Criteria in Solid Tumours (RECIST) 1.1 Criteria for Evaluating Response in Solid Tumours

RECIST version 1.1* will be used in this study for assessment of tumour response. While either CT or MRI may be utilized, as per RECIST 1.1, CT is the preferred imaging technique in this study.

* As published in the European Journal of Cancer:

E.A. Eisenhauer, P. Therasse, J. Bogaerts, L.H. Schwartz, D. Sargent, R. Ford, J. Dancey, S. Arbuck, S. Gwyther, M. Mooney, L. Rubinstein, L. Shankar, L. Dodd, R. Kaplan, D. Lacombe, J. Verweij. New response evaluation criteria in solid tumours: Revised RECIST guideline (version 1.1). Eur J Cancer. 2009 Jan;45(2):228-47.

12.5 APPENDIX 5: Identification, evaluation and management of ECIs

ECI	Grade	Action to be taken	Supportive Care
Pneumonitis –	Grade 1 (Asymptomatic)	• No action	• Intervention not indicated
	Grade 2	• Withhold pembrolizumab, may restart if Grade 1 or	• 1-2mg/kg/day prednisone or equivalent. • Symptoms grade 1 or less, initiate steroid

		
 resolved within 12 weeks Consider bronchoscopy and biopsy/BAL, ID Consult and frequent chest x-ray for monitoring. Conduct in person evaluation twice a week 	
 taper for no less than 4 weeks. Permanently discontinue pembrolizumab if dose cannot be reduced to 10mg prednisone or less or equivalent per day within 12 weeks.
	Grade 3 and 4	
 Discontinue pembrolizumab Hospitalize patient Bronchoscopy with biopsy and/or BAL is recommended. 	
 methylprednisolone 125mg IV. Symptoms grade 1 or less initiate steroid taper for no less than 4 weeks 
 Prednisone 1 to 2 mg/kg/day or dexamethasone 4mg every 4 hours If IV steroids do not reduce initial symptoms within 48-72 hours treat with additional anti-inflammatory measures. At symptom relief discontinue anti-inflammatory and start steroid taper over 45-60 days. If symptoms worsen during this period refer to section 6 and 7.

 1st episode - May increase dosing interval by one week in subsequent cycles 2nd episode of - Pneumonitis Permanently discontinue pembrolizumab if upon re-challenge patient develops Pneumonitis ≥ Grade 2 			
Colitis	Grade 1 (Asymptomatic)	
 No action 	
 Intervention not indicated
	Grade 2 (For grade 2 diarrhoea that persists > 3 days)	
 Withhold pembrolizumab, may restart if Grade 1 or resolved within 12 weeks Symptomatic treatment 
 Consider GI consult & endoscopy to rule out colitis 	
 Prednisone 1-2mg/kg/day or equivalent Symptoms grade 1 or less, initiate steroid taper for no less than 4 weeks. Permanently discontinue pembrolizumab if dose cannot be reduced to 10mg or less of prednisone or equivalent per days within 12 weeks. If symptoms worsen or persist >1 week treat as grade 3.
	Grade 3	
 Withhold pembrolizumab Rule out bowel perforation Recommend gastroenterologist consult & biopsy with endoscopy 	
 methylprednisolone 125mg IV followed by prednisone 1 to 2 mg/kg/day or dexamethasone 4mg every 4 hours. Symptoms grade 1 or less initiate steroid taper for no less than 4 weeks. Taper 6-8 weeks in patients with diffuse or severe ulceration and/or bleeding If IV steroids do not reduce initial symptoms within 48-72 hours treat with additional anti-inflammatory measures. At symptom relief discontinue anti-inflammatory and initiate steroid taper over 45-60 days. If symptoms worsen during this period refer to Section 6 and 7.
	Grade 4	
 Discontinue pembrolizumab 	
 Manage as per grade 3
Endocrine –	Grade 1	
 No action 	
 Intervention not indicated

Hypo and hyperthyroidism	(Asymptomatic)		
	Grade 2 Hyperthyroidism and Grade 2- 4 Hypothyroidism	
 Monitor thyroid function until returned to baseline. Consider consultation with endocrinologist. Pembrolizumab can continue while on this treatment. 	
 Thyroid hormone and/or steroid replacement therapy. Hyper – non-selective beta blockers for initial therapy Hypo – thyroid hormone replacement therapy as per standard of care.
	Grade 3 Hyperthyroidism	
 Withhold pembrolizumab, may restart if Grade 1 or resolved within 12 weeks Rule out infection and sepsis. 	
 IV methylprednisolone 1-2mg/kg followed by prednisone 1-2mg/kg per day. Symptoms grade 1 or less initiate steroid taper for no less than 4 weeks. Replacement of appropriate hormones may be required. Permanently discontinue pembrolizumab if dose cannot be reduced to prednisone 10mg or less or equivalent per day within 12 weeks.
	Grade 4 Hyperthyroidism	
 Discontinue pembrolizumab 	
 Manage as per grade 3
Endocrine – Hypophysitis or other symptomatic endocrinopathy	Grade 1 (Asymptomatic)	
 No action 	
 Intervention not indicated
	Grade 2 – 4	
 Withhold pembrolizumab Rule out infection and sepsis. Monitor thyroid function until returned to baseline. Consider pituitary gland imaging Hypophysitis with clinically significant adrenal insufficiency and hypotension, dehydration, and electrolyte abnormalities (such as hyponatremia and hyperkalemia) constitutes adrenal crisis. Consider endocrinologist consult. 	
 Prednisone 40mg p.o. or equivalent per day. Symptoms grade 1 or less initiate steroid taper for no less than 4 weeks. Replacement of appropriate hormones may be required. Permanently discontinue pembrolizumab if dose cannot be reduced to prednisone 10mg or less or equivalent per day within 12 weeks.
Type 1 Diabetes Mellitus and ≥ grade 3 hyperglycaemia	Type 1 Diabetes Mellitus and ≥ grade 3 hyperglycaemia	
 Hold pembrolizumab if new onset of diabetes or grade 3-4 hyperglycaemia with evidence of beta cell failure. Consultation with endocrinologist Consider islet cell antibodies and antibodies 	
 Insulin replacement therapy is recommended for Type I diabetes mellitus and for Grade 3-4 hyperglycaemia associated with metabolic acidosis or ketonuria. Evaluate patients with serum glucose and a metabolic panel, urine ketones, glycosylated haemoglobin, and C-peptide.

		to GAD, IA-2 ZnT8 and insulin.	
Hematologic	Grade 1 (Asymptomatic)	
 No action 	
 Intervention not indicated
	Grade 2	
 Withhold pembrolizumab, may restart if Grade 1 or resolved within 12 weeks Consider Haematology consultation 	
 Prednisone 1-2mg/kg daily Permanently discontinue pembrolizumab if dose cannot be reduced to prednisone 10mg or less or equivalent per day within 12 weeks.
	Grade 3	
 Withhold pembrolizumab, may restart if Grade 1 or resolved within 12 weeks Recommend Haematology consultation 	
 IV methylprednisolone 125mg or Prednisone 1-2mg/kg p.o. (or equivalent) as appropriate. Permanently discontinue pembrolizumab if corticosteroid dose cannot be reduced to prednisone 10mg or less or equivalent per day within 12 weeks.
	Grade 4	
 Discontinue pembrolizumab Recommend Haematology consultation 	
 IV methylprednisolone 125mg or Prednisone 1-2mg/kg p.o. (or equivalent) as appropriate.
Hepatic – Drug induced Liver Injury (DILI). Please refer to sections 6 and 7 for definitions of (DILI)	Grade 1 (Asymptomatic)	
 No action 	
 Intervention not indicated
	Grade 2	
 Report liver toxicity ECIs within 24 hours, as detailed in section 7.6.2. Withhold Pembrolizumab if AST or ALT >3.0 to 5.0 X ULN and/or total bilirubin is >1.5 to 3.0 X ULN Monitoring Liver function until values return to baseline 	
 0.5-1mg/kg/day methylprednisolone 125mg or oral equivalent. LFT grade 1 or less initiate steroid taper for no less than 4 weeks. Consider prophylactic antibiotics and resume pembrolizumab. Permanently discontinue pembrolizumab if dose cannot be reduced to prednisone 10mg or less or equivalent per day within 12 weeks. Permanently discontinue pembrolizumab for patients with liver mets who begin treatment with grade 2 elevation of AST or ALT and AST or ALT increase ≥50% relative to baseline and lasts ≥ 1 week.
	Grade 3	
 Report liver toxicity ECIs within 24 hours, as detailed in section 7.6.2. Discontinue pembrolizumab if AST or ALT > 5.0 X ULN and/or total bilirubin is >3.0 X ULN Consider consultation and biopsy to establish etiology 	
 High dose IV glucocorticosteroids for 24-48hours. Symptoms grade 1 or less initiate steroid taper for no less than 4 weeks 
 prednisone 1 to 2 mg/kg/day or dexamethasone 4mg every 4 hours. If serum transaminase levels do not decrease or symptoms worsen please refer to section 6 and 7. Permanently discontinue pembrolizumab if dose cannot be reduced to prednisone 10mg or less or equivalent per day within 12 weeks.
	Grade 4	
 Report liver toxicity ECIs within 24 hours, as detailed in section 7.6.2. 	
 Manage as per grade 3

		
 • Discontinue pembrolizumab 	
Neurologic	Grade 1 (Asymptomatic)	
 • No action 	
 • Intervention not indicated
	Grade 2	
 • Consider withholding pembrolizumab • Consider Neurology consult and biopsy for diagnosis. 	
 • Consider 1-2mg/kg daily of prednisone as appropriate • Permanently discontinue pembrolizumab if dose cannot be reduced to prednisone 10mg or less or equivalent per day within 12 weeks.
	Grade 3 and 4	
 • Discontinue pembrolizumab • Obtain Neurology consultation • Consider biopsy for diagnosis. 	
 • 1-2mg/kg daily of prednisone or equivalent. • If condition worsens consider IVIG or other immunosuppressive therapies • Symptoms grade 1 or less, initiate steroid taper for no less than 4 weeks.
Ocular	Grade 1 (Asymptomatic)	
 • No action 	
 • Intervention not indicated
	Grade 2	
 • Evaluation by ophthalmologist recommended 	
 • Topical steroids – 1% prednisolone acetate suspension and iridocyclitics • Permanently discontinue IF symptoms persist despite treatment.
	Grade 3	
 • Evaluation by ophthalmologist recommended • Withhold pembrolizumab & consider discontinuation. 	
 • 1-2mg/kg of prednisone daily. • Symptoms grade 1 or less initiate steroid taper for no less than 4 weeks. • Permanently discontinue pembrolizumab if dose cannot be reduced to prednisone 10mg or less or equivalent per day within 12 weeks.
	Grade 4	
 • Evaluation by ophthalmologist recommended • Permanently discontinue pembrolizumab 	Manage as per grade 3
Renal	Grade 1 (Asymptomatic)	
 • No action 	
 • Intervention not indicated
	Grade 2	
 • Withhold Pembrolizumab 	
 • 1-2mg/kg of prednisone daily. • Permanently discontinue pembrolizumab if dose cannot be reduced to prednisone 10mg or less or equivalent per day within 12 weeks.
	Grade 3 and 4	
 • Discontinue Pembrolizumab • Renal consultation and biopsy as appropriate 	
 • 1-2mg/kg of prednisone daily. • Symptoms grade 1 or less initiate steroid taper for no less than 4 weeks.
Skin – Rash and pruritus	Grade 1 (Asymptomatic)	
 • No action 	
 • Intervention not indicated
	Grade 2	
 • Symptomatic treatment 	
 • Topical glucocorticosteroids or urea-containing cream in combination with oral anti-pruritics • Treatment with oral steroids at PIs discretion

Skin Dermatitis exfoliative, erythema mulitforme, Stevens Johnson syndrome, toxic epidermal necrolysis.	Grade 3	
 Withhold Pembrolizumab Consider dermatology consult & biopsy for diagnosis. 	
 1mg/kg/day prednisone or equivalent or dexamethasone 4mg 4xdaily Symptoms grade 1 or less, initiate steroid taper for no less than 4 weeks. Permanently discontinue pembrolizumab if dose cannot be reduced to prednisone 10mg or less or equivalent per day within 12 weeks.
	Grade 4	
 Discontinue pembrolizumab Dermatology consultation Consider biopsy for diagnosis & clinical photographs 	
 Initiate steroids starting with 1-2mg/kg prednisone or equivalent.. Symptoms grade 1 or less, initiate steroid taper for no less than 4 weeks.
	Grade 1 (Asymptomatic)	
 No action 	
 Intervention not indicated
	Grade 2	
 Symptomatic treatment 	
 Topical glucocorticosteroids or urea-containing cream in combination with oral anti-pruritics. Treatment with oral steroids at PIs discretion
	Grade 3	
 Withhold Pembrolizumab Consider dermatology consultation and biopsy for diagnosis. 	
 1mg/kg/day prednisone or equivalent or dexamethasone 4mg 4xdaily. Symptoms grade 1 or less initiate steroid taper for no less than 4 weeks. Permanently discontinue pembrolizumab if dose cannot be reduced to prednisone 10mg or less or equivalent per day within 12 weeks.
	Grade 4	
 Discontinue pembrolizumab Dermatology consultation Consider biopsy for diagnosis & clinical photographs 	
 Initiate steroids starting with 1-2mg/kg prednisone or equivalent.. Symptoms grade 1 or less, initiate steroid taper for no less than 4 weeks.

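### The Appendix 5 instruction for Grade 2 liver toxicity gives two methylprednisolone doses without saying how they relate, and no other section settles the dose

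*Combined protocol and SAP*

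**What the plan says.** The supportive-care cell for hepatic Grade 2 in Appendix 5 (Section 12.5) opens with "0.5-1mg/kg/day methylprednisolone 125mg or oral equivalent". It goes on to a taper of at least four weeks, and to permanent discontinuation of pembrolizumab if the steroid cannot be brought down to 10 mg of prednisone within 12 weeks. The hepatic Grade 3 step is "High dose IV glucocorticosteroids for 24-48hours", followed by a taper.

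Six other Appendix 5 rows that cover Grade 2 state a systemic steroid dose, and each states exactly one:

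- pneumonitis: "1-2mg/kg/day prednisone or equivalent"
- colitis: "Prednisone 1-2mg/kg/day or equivalent"
- hypophysitis, Grade 2-4: "Prednisone 40mg p.o. or equivalent per day"
- haematologic: "Prednisone 1-2mg/kg daily"
- neurologic: "Consider 1-2mg/kg daily of prednisone as appropriate"
- renal: "1-2mg/kg of prednisone daily"

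Table 13 in Section 7.6.1 classifies hepatic events as events of clinical interest from Grade 2. Section 6.6 refers the site to Appendix 5 for managing such events when they are judged to be associated with the study drug.

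**The concern.** The bullet cannot be followed as a single regimen. It gives two amounts of one drug, and the phrase about an oral equivalent does not say which amount is to be matched. Three readings are open:

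1. 125 mg every day.
2. One 125 mg dose, then 0.5-1 mg/kg/day.
3. A choice between the two.

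Grade 2 is the first hepatic grade with a treatment instruction, since Grade 1 calls for no action. Two careful physicians could therefore give the same patient clearly different amounts of steroid. The steroid course also bears on whether pembrolizumab continues, because the same cell stops the drug permanently if the taper target is missed.

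**Working it through.** **Inputs.** The doses of 0.5-1 mg/kg/day and 125 mg come from the hepatic Grade 2 cell. The comparison range of 1-2 mg/kg comes from the other Grade 2 rows. The documents give no body weights, so 50, 70 and 90 kg are assumed. The seven-day window used below is also an assumption.

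**Could the two figures be the same daily dose?** The weight at which they agree is 125 mg divided by the mg/kg dose: 125/1.0 = 125 kg and 125/0.5 = 250 kg. Outside 125-250 kg they are different doses.

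**Size of the difference.** The weight-based dose is 0.5 × weight to 1 × weight.

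- *Daily reading:* the ratio is 125 divided by the weight-based daily dose.
- *Single first dose:* the ratio is (125 + 6 × daily dose) / (7 × daily dose).

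| Weight | Weight-based dose, mg/day | Ratio if 125 mg is daily | Seven-day ratio if 125 mg is given once |
|---|---|---|---|
| 50 kg | 25-50 | 125/50 = 2.5 to 125/25 = 5.0 | 425/350 = 1.21 to 275/175 = 1.57 |
| 70 kg | 35-70 | 125/70 = 1.79 to 125/35 = 3.57 | 545/490 = 1.11 to 335/245 = 1.37 |
| 90 kg | 45-90 | 125/90 = 1.39 to 125/45 = 2.78 | 665/630 = 1.06 to 395/315 = 1.25 |

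**Is 125 mg out of line with other Grade 2 rows?** Five of those rows use 1-2 mg/kg prednisone. Taken mg for mg (the documents give no conversion between the two drugs), 125 mg lies in that range from 125/2 = 62.5 kg to 125/1 = 125 kg. It is inside at 70 and 90 kg and above it at 50 kg (2.5 mg/kg). So 125 mg is outside this cell's own range, but not clearly outside what the table uses at Grade 2.

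**Does the rest of Appendix 5 show the intent?** Seven rows covering Grade 2 state a systemic steroid dose, and hepatic is the only one with two. A 125 mg dose appears five times: pneumonitis Grade 3-4, colitis Grade 3, haematologic Grades 3 and 4, and hepatic Grade 2. The other four are all Grade 3 or 4. Where a single bullet pairs 125 mg with a weight-based dose, the link is written out: *followed by* in colitis Grade 3, *or* in haematologic Grades 3 and 4. The hepatic Grade 2 bullet has no link.

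**Does another section set the dose?**

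- Table 10 (Section 6.3.9.2): hold, restart and stop rules only for Grade 2 AST, ALT or bilirubin.
- Section 6.5.1.1: its mg/kg doses are for enterocolitis.
- Table 12 (Section 6.6): Grade 2 says to consider steroids, with no dose. The 1 to 2 mg/kg stands in the Grade 3-4 row.
- Immune-mediated hepatitis paragraph (Section 6.6): steroids are to be given, with no dose.
- Sections 7.6.1 and 7.6.2: definition and reporting only.

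None of them resolves the bullet, and Section 6.6 leads back to it.

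**The case against.** The strongest objection is that this may be an artefact. The text was read from a PDF table, Appendix 5 shows broken cells and rows nearby, and the defect is one missing word. That cannot be excluded, and the original must be checked before anything is changed. But the visible damage lies at cell and row boundaries. The neighbouring bullets in this cell are intact, and no word is shown to be lost within a line anywhere in the table.

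Second, this is an ambiguity rather than a proven wrong figure. Under two of the three readings both doses can be valid and only the link is missing. Only the daily reading conflicts, and the largest ratio, 5.0, needs that reading at 50 kg and the lowest dose. That is fair, and it is why both readings are sized above.

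Third, the table does not always state the link. In pneumonitis Grade 3-4, 125 mg is followed by a separate prednisone entry with no connector. That limits the drafting contrast to doses paired within one bullet.

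Fourth, there are safeguards. Section 6.6 calls Appendix 5 recommendations and directs management questions to the sponsor. Section 6.5.1 leaves supportive care to the treating investigator. Liver toxicity events of clinical interest are reported within 24 hours, and the trial has one site. These lower the risk, but they do not make the written dose clear.

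**Conclusion.** The concern holds. The hepatic Grade 2 bullet gives two unlinked doses of one drug, and nothing else in the protocol says which applies. At assumed weights of 50 to 90 kg, the possible excess over the weight-based dose runs from 1.1 times (single first dose, seven days) to 5.0 times (daily 125 mg).

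Severity is minor. The matter is patient safety alone, harm is not shown, and no dose-limiting toxicity rule, endpoint, sample size or analysis depends on it. Confidence is moderate because a connector may have been lost in the text. The documents give no rate of Grade 2 liver events, so the number of patients affected is not estimated.

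**What to change.** Check the original table for a lost connector, have the clinical team confirm the intended dose against its source, and state one regimen.

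- **Best fit to the table:** delete the 125 mg, leaving *0.5-1 mg/kg/day methylprednisolone or oral equivalent*. Every other 125 mg entry is Grade 3 or 4, and high-dose IV treatment is the hepatic Grade 3 step. This is an inference, since the documents do not say which figure was meant.
- **If a starting dose was meant:** write *125 mg IV once, followed by 0.5-1 mg/kg/day*.
- **If a choice was meant:** write *or* between the two and say when each applies.

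The cost is a wording correction to one bullet. No hold or stop rule changes, and no patients, visits or analyses are added.
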